PRIMARY FEASIBILITY ENDPOINT:	The proportion of subjects that achieve Acute Procedural Success (APS) defined as the percutaneous endocardial creation of a complete, electrically isolating set of lesions around the ostia of the pulmonary veins (PVI) using the FARAPULSE Endocardial Multi Ablation System during the Index Procedure, as clinically assessed by entrance and/or exit block performed \geq 20 minutes after the last PVI lesion is made.

SECONDARY FEASIBILITY ENDPOINTS:	
1. The proportion of subjects who undergo the protocol-specified 75-Day Remapping Procedure and achieve Chronic Procedural Success (CPS) defined as persistent electrical isolation of all initially ablated pulmonary veins. Chronic Procedural Success will be subdivided by Index Procedure only CPS and Reablated CPS subjects.2. The proportion of attempted subjects that achieve Acute CTI Success, defined as the creation of bi-directional electrical block across the cavotricuspid isthmus using the investigational devices using the FARAPULSE Endocardial Multi Ablation System during the Index Procedure.3. Durability of the CTI and/or other extra-PV lesion set(s), when applicable. Durability is defined as unaltered integrity of each such lesion assessed at the Remapping Procedure.4. The proportion of subjects that achieve Therapeutic Success, defined as freedom from:
a. Post Blanking Period through assessment: occurrence of AF, AFL or AT or ablation for AF/AFL/AT using the study deviceb. At any time: ablation for AF/AFL/AT with a nonstudy device 
Therapeutic Success will be assessed from the end of the 90-day Blanking Period through Months 6 and 12 and will be subdivided by on / off AFDs (Atrial Fibrillation Drugs) post-Blanking Period.

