5.5 Imputation for Missing Data

Imputations for missing data in (e.g., withdrawn subjects, loss to follow-up, missing data) will not be performed. Analyses will be performed with all available data only.

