2.3.1. Databases

The Remapping at 75 Days, recurrence and Additional endpoints analysis will be based on the MDT Excel file sent by sponsor, which will contain:

- Received ablation at remap"
- RF/PFA ablation at remap
- Early recurrence of atrial fibrillation (AF)
- AF status
- AF km days"
- Atrial fibrillation/ Atrial flutter / Atrial tachycardia (AF/AFL/AT) status"
- AF/AFL/AT km (days)
- Transtelephonic monitor (TTM) weeks expected
- TTM weeks received
- Number TTM transmissions
- 6-month holter
- 12-month holter
- Radiofrequency (RF) touchup

CONFIDENTIEL / CONFIDENTIAL

Toute reproduction ou distribution, totale ou partielle, de ce document, sans autorisation préalable de ICON PLC est interdite.
Reproduction and distribution of this document, in whole or in part, is strictly forbidden without prior authorization from ICON PLC.

	STATISTICAL ANALYSIS PLAN	FARAPULSE PersAFOne SAP V1.0 PERSAFONE Page 15 /49
---	----------------------------------	--

- Ablation (ABL) >90 days"
- Class I/III antiarrhythmics drug (AAD) >90 days
- Amiodarone
- Direct current cardioversion (DCCV) >90 days
- Arrhythmia-related (AF, AFL, AT) hospitalization

The Excel file sent by the Sponsor will have the same structure (in terms of variables names, labels, formats) for each analysis to ensure the continuity of the programming.

All other analysis will be done on the e-CRF clinical database.

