IF Anatomical Structure/Area other specification 1 **IN** ("POSTERIOR WALL" "LA POSTERIOR WALL" "LAPW" "PA WALL" "BOX POSTERIOR WALL") **AND** Other 1 Lesion durable = 'yes' **OR** Anatomical Structure/Area other specification 2 **IN** ("POSTERIOR WALL" "LA POSTERIOR WALL" "LAPW" "PA WALL" "BOX POSTERIOR WALL") **AND** Other 2 Lesion durable = 'Yes' in **Follow-up 3D electroanatomical mapping form (RM)** **THEN** LAPW chronic isolation= 'Yes'
ELSE LAPW chronic isolation = 'No'
- Derived criteria "Number of veins durably isolated" will be defined as follows:
SUM of [LSPV chronic isolation='Yes', LIPV chronic isolation='Yes', LCPV chronic isolation='Yes', RSPV chronic isolation='Yes', RIPV chronic isolation='Yes', RMPV chronic isolation ='Yes'] in **Follow-up 3D electroanatomical mapping form (RM)**
- Derived criteria "Number of veins with gaps" will be defined as follows:
SUM of [LSPV chronic isolation='No', LIPV chronic isolation=' No', LCPV chronic isolation=' No', RSPV chronic isolation=' No', RIPV chronic isolation=' No', RMPV Chronic isolation = 'No'] in **Follow-up 3D electroanatomical mapping form (RM)**

6 and 12 Months follow up

- Derived criteria "TTM compliance (%) (calculated)" will be defined as follows:
(TTM weeks received /TTM weeks expected) *100 in **MDT excel file**
- Derived criteria "Holter compliance (%) at 6 months" will be defined as follows:

CONFIDENTIEL / CONFIDENTIAL

Toute reproduction ou distribution, totale ou partielle, de ce document, sans autorisation préalable de ICON PLC est interdite.
Reproduction and distribution of this document, in whole or in part, is strictly forbidden without prior authorization from ICON PLC.

	STATISTICAL ANALYSIS PLAN	FARAPULSE PersAFOne SAP V1.0 PERSAFONE Page 22 /49
---	----------------------------------	--

IF 6mo Holter in ('AF', 'none', 'SVT') in **MDT excel file** **THEN** Holter compliance (%) at 6 months = 'Yes'

ELSE IF 6mo Holter in ('MISSING') in **MDT excel file** **THEN** Holter compliance (%) at 6 months='No'

- Derived criteria "Holter compliance (%) at 12 months" will be defined as follows:

IF 12mo Holter in ('AF', 'none', 'SVT') in **MDT excel file** **THEN** Holter compliance (%) at 12 months = 'Yes'

ELSE IF 12mo Holter in ('MISSING') in **MDT excel file** **THEN** Holter compliance (%) at 12 months='No'

- Derived criteria "Freedom from AF/AFL/AT" will be defined as follows:

IF AF/AFL/AT status =0 in **MDT excel file** **THEN** Freedom from AF/AFL/AT ='Yes'

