ELSE Freedom from AF/AFL/AT ='No'

- Derived criteria "Freedom from AF/AFL/AT with Class I/III AAD >90 days" will be defined as follows:

IF AF/AFL/AT status =0 **AND** Class I/III AAD >90 days =1 in **MDT excel file** **THEN** Freedom from AF/AFL/AT with Class I/III AAD >90 days ='Yes'

ELSE Freedom from AF/AFL/AT with Class I/III AAD >90 days ='No'

- Derived criteria "Freedom from AF/AFL/AT without Class I/III AAD >90 days" will be defined as follows:

IF AF/AFL/AT status =0 **AND** Class I/III AAD >90 days =0 in **MDT excel file** **THEN** Freedom from AF/AFL/AT without Class I/III AAD >90 days ='Yes'

ELSE Freedom from AF/AFL/AT without Class I/III AAD >90 days ='No'

- Derived criteria "Freedom from AF" will be defined as follows:

IF AF status =0 in **MDT excel file** **THEN** Freedom from AF ='Yes'

ELSE Freedom from AF ='No'

- Derived criteria "Freedom from AF with Class I/III AAD >90 days" will be defined as follows:

IF AF status =0 **AND** Class I/III AAD >90 days =1 in **MDT excel file** **THEN** Freedom from AF with Class I/III AAD >90 days ='Yes'

ELSE Freedom from AF with Class I/III AAD >90 days ='No'

- Derived criteria "Freedom from AF without Class I/III AAD >90 days" will be defined as follows:

IF AF status =0 **AND** Class I/III AAD >90 days =0 in **MDT excel file** **THEN** Freedom from AF without Class I/III AAD >90 days ='Yes'

ELSE Freedom from AF without Class I/III AAD >90 days ='No'

- Derived criteria "Freedom from AF/AFL/AT, no DCCV>90 days, no RF, no ablation >90 days" will be defined as follows:

CONFIDENTIEL / CONFIDENTIAL

Toute reproduction ou distribution, totale ou partielle, de ce document, sans autorisation préalable de ICON PLC est interdite.
Reproduction and distribution of this document, in whole or in part, is strictly forbidden without prior authorization from ICON PLC.

	STATISTICAL ANALYSIS PLAN	FARAPULSE PersAFOne SAP V1.0 PERSAFONE Page 23 /49
---	----------------------------------	--

IF AF/AFL/AT status =0 **AND** DCCV90D=0 **AND** RF touch up=0 **AND** ABL>90 day=0 in **MDT excel file** **THEN** Freedom from AF/AFL/AT, no DCCV>90 days, no RF, no ablation >90 days ='Yes'

ELSE Freedom from AF/AFL/AT, no DCCV>90 days, no RF, no ablation >90 days ='No'

- Derived criteria "Freedom from AF/AFL/AT, no DCCV>90 days, no RF, no ablation >90 days with Class I/III AAD >90 days" will be defined as follows:

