- Derived criteria "Durability of Left atrial roof line at remap" will be defined as follows:
IF Left atrial roof line lesion durable ='Yes' in **Follow-up 3D electroanatomical mapping form (RM)** **THEN** Durability of Left atrial roof line at remap = 'Yes'
ELSE IF Left atrial roof line lesion durable ='No' in **Follow-up 3D electroanatomical mapping form (RM)** **THEN** Durability of Left atrial roof line at remap = 'No'
- Derived criteria "Durability of Left atrial Posterior line" will be defined as follows:
IF Left atrial Posterior line lesion durable ='Yes' in **Follow-up 3D electroanatomical mapping form (RM)** **THEN** Durability of Left atrial Posterior line at remap = 'Yes'
ELSE IF Left atrial Posterior line lesion durable ='No' in **Follow-up 3D electroanatomical mapping form (RM)** **THEN** Durability of Left atrial Posterior line at remap = 'No'
- Derived criteria "Therapeutic Success ON/OFF AAD" will be defined as follows:

CONFIDENTIEL / CONFIDENTIAL

Toute reproduction ou distribution, totale ou partielle, de ce document, sans autorisation préalable de ICON PLC est interdite.
Reproduction and distribution of this document, in whole or in part, is strictly forbidden without prior authorization from ICON PLC.

IF "AF/AFL/AT status"= 0 **AND** "RF touchup"= 0 **AND** "ABL >90 days" = 0 **in MDT excel file**
THEN therapeutic success='Yes'
ELSE therapeutic success='No'

- Derived criteria "Therapeutic Success Off ADD" will be defined as follows:
IF Therapeutic success ='Yes' **AND** Class I/III AAD>90days=0 **in MDT excel file** **THEN** therapeutic success Off ADD ='YES'
ELSE IF Therapeutic success ='No' **AND** Class I/III AAD>90days=0 **in MDT excel file** **THEN** **THEN** therapeutic success Off ADD ='NO'
- Derived criteria "Therapeutic Success On ADD" will be defined as follows:
IF Therapeutic success ='Yes' **AND** Class I/III AAD>90days=1 **in MDT excel file** **THEN** therapeutic success On ADD ='No'
Else If Therapeutic success ='No' **AND** Class I/III AAD>90days=1 **in MDT excel file** **THEN** **THEN** therapeutic success On ADD ='No'

Additional endpoints

- Derived criteria "Proportion of all ablated pulmonary veins that are isolated at the Index Procedure using the study device" will be defined as follows:

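### SAP 2.5 scores 12-month freedom from arrhythmia from a status flag with no follow-up requirement; if early leavers carry status 0, they count as successes

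*SAP*

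**What the plan says.** **Endpoint.** The protocol (executive summary, and section 6.4 in near-identical words) states: "Therapeutic Success will be assessed from the end of the 90-day Blanking Period through Months 6 and 12". SAP 2.4.6.2 repeats this.

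**Freedom rule (SAP 2.5).** "IF AF/AFL/AT status =0 in MDT excel file THEN Freedom from AF/AFL/AT ='Yes", with the fallback "ELSE Freedom from AF/AFL/AT ='No". The other freedom variables add conditions on AAD use, cardioversion, RF touch-up or late ablation, but none on follow-up time.

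**Therapeutic Success rule (SAP 2.5).** Success follows "IF 'AF/AFL/AT status'= 0 AND 'RF touchup'= 0 AND 'ABL >90 days' = 0 in MDT excel file". The off-AAD version builds on this result. The on-AAD version assigns "therapeutic success On ADD ='No" in both of its branches.

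**Source file (SAP 2.3.1, Databases).** The file lists "Atrial tachycardia (AF/AFL/AT) status" next to "AF/AFL/AT km (days", and a similar pair for AF alone. It gives no codes, no time origin, and no value for withdrawn or lost subjects.

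**Reporting.** Table 7, titled as a 12-month table, and Table 13 show n/N on the ITT population. SAP 2.1.4 plans Kaplan-Meier curves with rates at 30, 90, 180 and 365 days; Graphs 2 to 10 are freedom curves.

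**Missing data.** Protocol 5.5: "Analyses will be performed with all available data only". SAP 2.1.2 likewise plans no replacement of missing values. SAP 2.5 opens by making a derived value missing when one of its inputs is missing.

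**The concern.** A status flag paired with a time is a survival record: 0 says only that no event was seen up to the recorded day. The binary rules use the flag and ignore the time.

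Consider a subject who leaves on day 60. Recurrences through day 90 are not Therapeutic Failures (Protocol 3.11.3), and the event monitor is issued only at the 75-day remap (Protocol 3.11.4). This subject cannot register a post-blanking recurrence. With status 0 and the procedure flags at 0, the subject is nevertheless a 12-month success. In effect that is a favourable imputation, in a plan that says it makes none.

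Worse retention would then flatter the result, and one file could yield two different 12-month figures: an n/N rate in the tables and a lower Kaplan-Meier rate beside the graphs. These are the trial's 12-month effectiveness results, and Protocol 5.3 says the findings will inform later studies.

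**Working it through.** The documents state no dropout rate, recurrence rate or expected success rate, so there is no planned figure to reproduce. The counts below are assumptions, except N = 40 (Protocol 5.3) and N = 25 (the shells of SAP Tables 5 and 19).

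**Notation.** N subjects; f recorded recurrences; d early leavers with status 0; f1 recurrences before the exits.

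- SAP rule: (N − f)/N
- Kaplan-Meier, all exits at one time: (N − f1)/N × (N − f − d)/(N − f1 − d)
- Observed subjects only: (N − f − d)/(N − d). This equals Kaplan-Meier when f1 = 0.
- Leavers counted as failures: (N − f − d)/N

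**Direction.** For f > 0 and d > 0, f/N is smaller than f/(N − d), so the SAP rule always exceeds the observed-only rate. It exceeds Kaplan-Meier when at least one exit precedes a recurrence. It equals Kaplan-Meier with no early exits, or if every exit follows the last recurrence.

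**Example: N = 40, f = 12, d = 4.** SAP rule 28/40 = 70.0%; leavers as failures 24/40 = 60.0%. Kaplan-Meier, with recurrences assumed evenly spaced over days 110 to 340:

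| Exit day | f1 | Kaplan-Meier | SAP rule minus Kaplan-Meier |
|---|---|---|---|
| 60 | 0 | 24/36 = 66.7% | 3.3 points |
| 180 | 4 | 36/40 × 24/32 = 67.5% | 2.5 points |
| 240 | 7 | 33/40 × 24/29 = 68.3% | 1.7 points |
| 300 | 10 | 30/40 × 24/26 = 69.2% | 0.8 points |

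**Example: N = 25, f = 7, d = 3, exits before day 90.** SAP rule 18/25 = 72.0%; Kaplan-Meier 15/22 = 68.2%; leavers as failures 15/25 = 60.0%.

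**Range at N = 40, exits before any recurrence.** Smallest gap tried (f = 5, d = 2): 35/40 = 87.5% against 33/38 = 86.8%, or 0.7 points. Largest (f = 15, d = 8): 25/40 = 62.5% against 17/32 = 53.1%, or 9.4 points.

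**Expected value.** Assume true 12-month freedom of 70%, a constant hazard after day 90, and 10% dropout unrelated to recurrence.

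- All leave at day 90: 0.9 × 70% + 0.1 × 100% = 73.0%.
- All leave at day 180: freedom at exit is 0.70^(90/275) = 89.0%, so 0.9 × 70% + 0.1 × 89.0% = 71.9%.

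**If leavers' status is blank.** The opening rule of SAP 2.5 makes the result missing, the rate becomes the observed-only rate, and this inflation is absent. Read literally, however, the fallback "ELSE Freedom from AF/AFL/AT ='No" would make such a subject a failure. The SAP does not say which applies.

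**The case against.** The strongest objection is that status 0 for early leavers is an inference. The SAP lists variable names only, and a blank would be handled as missing. A day-60 leaver's late-ablation flag might also be blank, which would remove that subject from Therapeutic Success. This stands as a limit on certainty. It does not remove the point: Kaplan-Meier censoring needs a non-event code, and 0 is the only one the SAP uses.

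The SAP already plans Kaplan-Meier curves and reports visit attendance, exit reasons, follow-up time, and TTM and Holter compliance, so attrition would be visible. That is fair, but Tables 7 and 13 still report n/N. No listed graph matches Therapeutic Success either: Graph 6 comes closest but also counts late cardioversion. Time to Therapeutic Failure appears in Table 11 only as a mean, median and quartiles.

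The effect may also be small against sampling error: the exact 95% interval for 28/40 is 53.5% to 83.4%. That is true, but an avoidable bias in one direction is not excused by a wide interval.

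A reader might infer that dropout raises every arrhythmia rate, or that n/N must exceed Kaplan-Meier. The documents support neither. On-AAD Therapeutic Success is never scored as a success, the curves can censor leavers, and the two estimates can coincide.

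**Conclusion.** The gap in the rules is certain: SAP 2.5 asks for no follow-up to month 12 before it scores a 12-month success. The upward bias is conditional on early leavers carrying status 0, which the pairing with Kaplan-Meier days makes likely but does not establish. A reader who takes that coding as stated fact goes beyond the text.

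If it holds, the exposed results are the freedom proportions in Table 7 and the overall and off-AAD Therapeutic Success proportions in Table 13. Their size cannot be determined from the documents. In the assumed scenarios at N = 40 with exits before any recurrence, the excess runs from 0.7 to 9.4 points; it shrinks with later exit and is zero with complete follow-up.

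These are secondary, descriptive results with no hypothesis test. The primary endpoints, Acute Procedural Success and the Composite Safety Endpoint, do not use this flag. The point should be fixed; confidence is moderate.

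**What to change.** 1. **Define the variables.** In SAP 2.3.1 (Databases), state that 1 = event and 0 = censored at the last rhythm observation, and give the time origin of the Kaplan-Meier days.
2. **Change the reported estimate.** In Tables 7 and 13, give the Kaplan-Meier estimate with 95% CI at day 365, and at day 180 for month 6, as the freedom and success rate.
3. **Cover Therapeutic Success.** Add a time-to-failure analysis using exactly its definition.
4. **If n/N rows are kept,** show how many status-0 subjects have fewer than 335 days (365 − 30, the lower limit of the 12-month window, counting from the index procedure). Give the rate with them as successes and as failures, as bounds (70.0% and 60.0% in the N = 40 example). Do not drop them: removing short-follow-up non-events while keeping every failure biases the rate downward. With day-300 exits, that gives 24/36 = 66.7% against Kaplan-Meier 69.2%.
5. **Month 6.** Count only events dated by the month-6 time point. The single status flag would otherwise make a subject who first recurs on day 300 a month-6 failure.

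The cost is minor SAP wording and programming, with no new data. The reported rate may be slightly lower.

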2.4.4. Remapping at 75 Days

Descriptive statistical data will be used to draw up a recapitulation of the follow-up details at 75-day Visit and Remapping Procedure.

The following data will be presented on the ITT population:

Days follow up at remap, Durable PVI, LSPV chronic isolation, LIPV chronic isolation, LCPV chronic isolation, RSPV chronic isolation, RIPV chronic isolation, RMPV chronic isolation, CTI chronic isolation, LAPW chronic isolation, Number of veins durably isolated, Number of veins with gaps.

2.4.5. 6 and 12 Months follow up

Descriptive statistical data will be used to draw up a recapitulation of the follow-up details at 6 and 12 Months follow up.

The following data will be presented on the ITT population:

TTM compliance, Holter compliance (6 month and 12 month), Freedom from AF/AFL/AT (for patient On AADs and on patient Off AADs), Freedom from AF (for patient On AADs and on patient Off AADs), Freedom from AF/AFL/AT, no DCCV>90 days, no RF, no ablation >90 days (for patient On AADs and on patient Off AADs), Freedom from AF, no DCCV>90 days, no RF, no ablation >90 days (for patient On AADs and on patient Off AADs).

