4.1.7. Table 7. Arrhythmia Recurrence at 12 Months

	ITT Population N = XX	
	Mean±S.D. Median (min, max) (Q1, Q3)	[95% CI]
TTM compliance	XX±X XX (XX, XX) (XX, XX)	[XX - XX]
	n/N (%)	[95% CI]
Holter compliance (6 month)	XX/XX (XX.X%)	[XX% - XX%]
Freedom from AF/AFL/AT	XX/XX (XX.X%)	[XX% - XX%]
	XX/XX (XX.X%)	[XX% - XX%]
On AADs	XX/XX (XX.X%)	[XX% - XX%]

CONFIDENTIEL / CONFIDENTIAL

Toute reproduction ou distribution, totale ou partielle, de ce document, sans autorisation préalable de ICON PLC est interdite.
Reproduction and distribution of this document, in whole or in part, is strictly forbidden without prior authorization from ICON PLC.

	STATISTICAL ANALYSIS PLAN	FARAPULSE PersAFOne SAP V1.0 PERSAFONE Page 39 /49
---	----------------------------------	--

Off AADs		
Freedom from AF	XX/XX (XX.X%)	[XX% - XX%]
	XX/XX (XX.X%)	[XX% - XX%]
On AADs	XX/XX (XX.X%)	[XX% - XX%]
Off AADs	XX/XX (XX.X%)	[XX% - XX%]
Freedom from AF/AFL/AT, no DCCV>90 days, no RF, no ablation >90 days	XX/XX (XX.X%)	[XX% - XX%]
On AADs	XX/XX (XX.X%)	[XX% - XX%]
Off AADs	XX/XX (XX.X%)	[XX% - XX%]
Freedom from AF, no DCCV>90 days, no RF, no ablation >90 days	XX/XX (XX.X%)	[XX% - XX%]
On AADs	XX/XX (XX.X%)	[XX% - XX%]
Off AADs	XX/XX (XX.X%)	[XX% - XX%]

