4.3. Graphs

4.3.1. Graph 1: Patient disposition

4.3.2. Graph 2: Freedom from AF/AFL/AT on ADDs

- Summary table

	Group 1 (N=XXX)
Nb of patients	XXX
Nb of patients with an event	XX (XX.X%)
Nb of patients without an event	XX (XX.X%)
Survival rate	XX %
Time to event (days)	
Median	XX
(95% CI)	(XX, XX)
25th-75th percentile	XXX – XXX
Range	X.XX - X.XX

CONFIDENTIEL / CONFIDENTIAL

Toute reproduction ou distribution, totale ou partielle, de ce document, sans autorisation préalable de ICON PLC est interdite.
Reproduction and distribution of this document, in whole or in part, is strictly forbidden without prior authorization from ICON PLC.

	STATISTICAL ANALYSIS PLAN	FARAPULSE PersAFOne SAP V1.0 PERSAFONE Page 49 /49
---	----------------------------------	--

- 4.3.3. Graph 3: Freedom from AF/AFL/AT off ADDs**
- 4.3.4. Graph 4: Freedom from AF on AADs**
- 4.3.5. Graph 5: Freedom from AF off AADs**
- 4.3.6. Graph 6: Freedom from AF/AFL/AT, no DCCV>90 days, no RF, no ablation >90 days**
- 4.3.7. Graph 7: Freedom from AF/AFL/AT, no DCCV>90 days, no RF, no ablation >90 days on AADS**
- 4.3.8. Graph 8: Freedom from AF/AFL/AT, no DCCV>90 days, no RF, no ablation >90 days off AADS**
- 4.3.9. Graph 9: Freedom from AF, no DCCV>90 days, no RF, no ablation >90 days on AADs**
- 4.3.10. Graph 10: Freedom from AF, no DCCV>90 days, no RF, no ablation >90 days off AADs**
- 4.3.11. Graph 11: Death**

CONFIDENTIEL / CONFIDENTIAL

Toute reproduction ou distribution, totale ou partielle, de ce document, sans autorisation préalable de ICON PLC est interdite.
Reproduction and distribution of this document, in whole or in part, is strictly forbidden without prior authorization from ICON PLC.

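### The eight On/Off-AAD freedom rules in SAP 2.5 count every subject of the other drug group as a failure, so the Table 7 sub-rows are not rates among patients on or off AADs

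*SAP*

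**What the plan says.** SAP 2.4.5 (6 and 12 Months follow up) lists, on the ITT population, "Freedom from AF/AFL/AT (for patient On AADs and on patient Off AADs"). It repeats the same split for three further measures: freedom from AF, and the two composites that also require no late cardioversion, no RF and no late ablation. These are the On and Off sub-rows of Table 7, "Arrhythmia Recurrence at 12 Months".

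SAP 2.5 derives the first On variable as Yes under "IF AF/AFL/AT status =0 AND Class I/III AAD >90 days =1 in MDT excel file", and otherwise applies "ELSE Freedom from AF/AFL/AT with Class I/III AAD >90 days ='No". The Off counterpart ends "ELSE Freedom from AF/AFL/AT without Class I/III AAD >90 days ='No", and the AF-only Off rule ends "ELSE Freedom from AF without Class I/III AAD >90 days ='No". The remaining rules follow the same pattern, giving four measures times two drug groups, or eight rules.

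Two general rules decide who is counted. SAP 2.1.3 calculates percentages on non-missing observations. The opening of SAP 2.5 sets a derived variable to missing only when one of its input items is missing.

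For Therapeutic Success Off AAD, SAP 2.5 uses a different construction. The result "therapeutic success Off ADD ='NO" is assigned only when the AAD flag is 0, so on-drug subjects receive no value.

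**The concern.** The text of SAP 2.4.5 describes rates within two patient groups. The derivation instead builds a joint outcome (free and in the group) and gives everyone else a No. A subject in the other drug group has a known AAD flag, so the missing-item rule does not remove that subject, and the No enters the denominator.

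A Table 7 sub-row would then mix two things: how often patients in the group stayed free of arrhythmia, and how many patients were in the group at all. A low On figure could mean poor outcomes on drug or simply few users. A reader who takes the label at face value would draw the wrong rate and an interval based on the wrong N. SAP 2.2 says the results will inform the design of further studies, so the figures may be reused.

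**Working it through.** The plan states no figure to reproduce: the Table 7 cells are empty shells and there is no sample size calculation. The check applies the rules literally and compares them with a within-group rate.

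**Inputs from the documents**
- Yes and No conditions: SAP 2.5, 6 and 12 Months follow up.
- Denominator: all non-missing values (SAP 2.1.3). Other-group subjects are non-missing (SAP 2.5, opening rule).
- Maximum N = 40 (Protocol 3.7).

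**Inputs assumed, because the documents do not give them**
- Share on AADs after day 90: 10% to 50%.
- Freedom of about 70% in each group.

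**Formulas.** Let s be the share on AADs, and p_on and p_off the freedom rates within each group.
- On row as written = s × p_on, where the within-group rate is p_on.
- Off row as written = (1 − s) × p_off, where the within-group rate is p_off.
- The two rows as written add up to the overall rate, s × p_on + (1 − s) × p_off. This shows that they are joint proportions.

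**Numbers, N = 40**

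| On / off AAD | On row as written | On, within group | Gap (points) | Off row as written | Off, within group | Gap (points) |
|---|---|---|---|---|---|---|
| 4 / 36 | 3/40 = 7.5% | 3/4 = 75.0% | 67.5 | 25/40 = 62.5% | 25/36 = 69.4% | 6.9 |
| 10 / 30 | 7/40 = 17.5% | 7/10 = 70.0% | 52.5 | 21/40 = 52.5% | 21/30 = 70.0% | 17.5 |
| 20 / 20 | 14/40 = 35.0% | 14/20 = 70.0% | 35.0 | 14/40 = 35.0% | 14/20 = 70.0% | 35.0 |

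In the middle scenario the exact 95% interval for the On row moves from 7.3–32.8% (7/40) to 34.8–93.3% (7/10). For the Off row it moves from 36.1–68.5% (21/40) to 50.6–85.3% (21/30). SAP 2.1.4 would use asymptotic intervals where their assumptions hold; that changes the limits but not the point estimates.

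**Ceiling.** If all 40 subjects were free and 10 were on AADs, the rows would print 10/40 = 25.0% and 30/40 = 75.0% instead of 100% and 100%.

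**Limits of the effect.** If nobody is on an AAD, the Off row is correct (28/40 = 70.0% either way), while the On row prints 0/40 = 0.0% where no rate exists. A group with no free subject shows 0% under either rule.

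**The eighth rule.** The AF-only composite without AADs tests AF status but assigns its result to the AF/AFL/AT composite variable. Taken literally, it overwrites the result of the sixth rule and leaves the AF-only composite Off row with no derived value.

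**The case against.** The strongest reply is that the derivation only creates a flag, and that SAP 2.4.5 says whom each row covers. If the On flag were tabulated only among patients on AADs, the stray No values would drop out and the row would be right. That result is correct, but it needs a subsetting step that appears neither in the derivation nor in the Table 7 shell, which is headed with the ITT N.

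A second reply is that being free and off drug, out of all ITT subjects, is a coherent measure. The variable names (with or without AAD) and the protocol's subdivision of Therapeutic Success in Section 6.4 fit rows that add up to the overall rate. But the SAP never states this as the target. The wording of SAP 2.4.5 and the group-restricted Off rule for Therapeutic Success both point the other way.

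A reader might also infer more than the documents support:
- **That Table 7 will contradict Table 13.** Therapeutic Success combines arrhythmia status, RF touch-up and late ablation, and no Table 7 measure has that definition. Table 13 is also a poor benchmark for the On row, because the Therapeutic Success On rule returns No in both branches.
- **That Table 7 will contradict the survival graphs.** SAP 4.3 gives titles such as "Freedom from AF/AFL/AT on ADDs" and one shell, without defining who is at risk in each curve. Graph 6 is not split by drug at all.
- **That drug-free freedom is the main efficacy signal.** Neither document says so. The primary feasibility endpoint is Acute Procedural Success, and the study tests no hypothesis.

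**Conclusion.** The point holds. As written, each On and Off sub-row of Table 7 is the proportion of all evaluable ITT subjects who are free and in that drug group, which is not the rate that SAP 2.4.5 requests. Both rows are understated whenever both groups are non-empty and each has at least one free subject.

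The direction follows from the rules alone. The size rests on the assumed on-drug share and freedom rates: about 35 to 68 points for the On row and about 7 to 35 for the Off row. The rows that are not split by drug use no AAD flag and stand as they are. Because the affected results are descriptive and not primary, this should be fixed but does not undermine the study's main conclusions.

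**What to change.** In SAP 2.5, define each On variable only for subjects whose flag for AAD use beyond 90 days is 1, and each Off variable only for those whose flag is 0. Within the group, assign Yes if the freedom condition is met and No if it is not. Subjects outside the group are not applicable. In Table 7, use the group size as N for each sub-row.

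Correct the eighth rule so that it writes to the AF-only composite variable without AADs, and not to the AF/AFL/AT one.

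If the sponsor also wants the proportion free and off AADs among all ITT subjects, add it as a separately labelled row.

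The cost is a change to eight derivation rules and the Table 7 shell, with the matching program lines. No new data are needed.
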